#### **Special Considerations related to AE Reporting**

The term "disease progression" alone should not be used when reporting AEs or SAEs, due to its lack of specificity. Rather, symptoms of disease progression should be reported. If death occurs as consequence of disease progression, this would be considered an outcome, and NOT an AE.

Example, a patient died due to a pulmonary hemorrhage secondary to tumor progression; an SAE report should be submitted with the event pulmonary hemorrhage notified as a Grade 5 (fatal).

Surgical procedures or other therapeutic interventions themselves are not AEs, but the condition for which the surgery/intervention is required is an AE and should be documented accordingly. Planned surgical measures and the condition(s) leading to these measures are not AEs if the condition(s) was (were) known before the period of observation and did not worsen during study. In the latter case, the condition should be reported as medical history.

Pregnancy is not an AE, although a patient will be withdrawn from the study if a pregnancy occurs. Refer to Section 10.3.4.1 for more information on reporting pregnancy events.

#### 10.1.2. Serious Adverse Events

An SAE is defined as any untoward medical occurrence that at any dose or due to study procedure causes or qualifies as the following:

- Results in death;
- Is life-threatening;
  - o "Life-threatening" means that the patient was at immediate risk of death at the time of the SAE; it does not refer to an SAE that hypothetically might have caused death if it were more severe.
- Requires hospitalization or prolongation of existing hospitalization;
  - This means that hospital inpatient admission or prolongation of hospital stay were required for the treatment of the SAE or that they occurred as a consequence of the event.
  - Visits to a hospital by ambulance or to the emergency room without admission will not be regarded as hospitalization unless the event fulfills any other of the serious criteria.
- Results in persistent or significant disability or incapacity;
  - o "Persistent or significant disability or incapacity" means a permanent or significant and substantial disruption of a person's ability to carry out normal life functions.
- Is a congenital anomaly or birth defect; and/or
- Is an important medical event.
  - Medical and scientific judgment should be exercised in deciding whether expedited reporting is appropriate in situations where none of the outcomes listed above occurred. Important medical events that may not be immediately life-threatening or result in death or hospitalization but may jeopardize the patient or may require intervention to prevent one of the other outcomes listed in the definition above should also usually be considered serious. Examples of such events include allergic bronchospasm requiring intensive treatment in an emergency room or at home, blood dyscrasias, convulsions that do not result in inpatient hospitalization, or repeated IRRs.

- o A diagnosis of new cancer/ malignant tumor during a treatment should always be considered as medically important.
- o For this study, any DLTs (as per Section 4.2.3.1) are considered as important medical events and should be reported as SAE.

All SAEs will be followed until resolution, the condition stabilizes or is considered chronic, the event is otherwise explained, or the patient is lost to follow-up or withdraws consent.

#### 10.2. Evaluation and Classification

#### **10.2.1.** Evaluation of Severity

All AEs (including SAEs) are to be accurately recorded on the AE page of the patient's eCRF. Each event will be graded for severity using the classifications of NCI CTCAE v5.0 (NCI 2017).

For events not addressed in the NCI CTCAE v5.0 classifications, the following grading will apply:

- Mild (Grade 1) Mild; asymptomatic or mild symptoms; clinical or diagnostic observations only; intervention not indicated.
- Moderate (Grade 2) Moderate; minimal, local, or noninvasive intervention indicated; limiting age-appropriate instrumental activity of daily living.
- Severe (Grade 3) Severe or medically significant but not immediately life-threatening; hospitalization or prolongation of hospitalization indicated; disabling; limiting self-care activity of daily living.
- Life-threatening (Grade 4) Life-threatening consequences; urgent intervention indicated.
- Fatal (Grade 5) Related to AE.

During initial dosing and its respective post-observation period, any clinical finding despite its severity that represents a change from baseline (e.g., mild skin reaction, fatigue, myalgia, etc.) shall be recorded and followed until resolution.

Likewise, any clinically significant finding identified during the remaining course of the study, which represents a change from baseline would be required to be recorded by the Investigator.

#### 10.2.2. Expectedness Assessment

The Sponsor will assess all SAEs whether they are expected or unexpected. An unexpected AE is any adverse drug event, the outcome, specificity, or severity of which is not consistent with those noted in the Reference Safety Information section of the current Investigator's Brochure (IB).

#### **10.2.3.** Causality Assessments

All AEs (including SAEs) will be assessed by the Investigator and Sponsor for the causal relationship of the AE to the study drug (AFM24, atezolizumab, or the combination of AFM24 and atezolizumab) using the following definitions described in Table 6.

For reporting and data analysis purposes, AEs reported with a causality assessment of "Definitely", "Probably", and "Possibly" are to be considered as "having a reasonable causal relationship" to

study drug. In case of disagreement between the Investigator and the Sponsor, the more conservative assessment will determine the reportability of the case.

**Table 6:** Relationship to Study Drug

	Relationship	Description		
1	Not related	This category applies to those AEs which, after careful consideration, are clearly and incontrovertibly due to extraneous causes (disease, environment, etc.).		
2	Unlikely (must have 2)	In general, this category can be considered applicable to those AEs which, after careful medical consideration at the time when they are evaluated, are judged to be unrelated to the study drug. An AE may be considered unlikely if or when:  1. It does not follow a reasonable temporal sequence from administration of the test drug.  2. It could readily have been produced by the patient's clinical state, environmental or toxic factors, or other modes of therapy administered to the patient.  3. It does not follow a known pattern of response to the test drug.  4. It does not reappear or worsen when the drug is re-administered.		
3	Possibly (must have 2)	This category applies to those AEs for which, after careful medical consideration at the time they are evaluated, a connection with the test drug administration appears unlikely but cannot be ruled out with certainty. An AE may be considered possibly related if or when:  1. It follows a reasonable temporal sequence from administration of the test drug.  2. It could not readily have been produced by the patient's clinical state, environmental or toxic factors, or other modes of therapy administered to the patient.  3. It follows a known pattern of response to the test drug.		
4	Probably (must have 3)	This category applies to those AEs for which, after careful medical consideration at the time they are evaluated, are felt with a high degree of certainty to be related to the test drug. An AE may be considered probably related if or when:  1. It follows a reasonable temporal sequence from administration of the test drug.  2. It could not be reasonably explained by the known characteristics of the patient's clinical state, environmental or toxic factors, or other modes of therapy administered to the patient.  3. It disappears or decreases on cessation or reduction in dose. There are important exceptions when an AE does not disappear upon discontinuation of the drug, yet drug-relatedness clearly exists (e.g., bone marrow depression, fixed drug eruptions, tardive dyskinesia).  4. It follows a known pattern of response to the test drug.		
5	Definitely (must have all)	This category applies to those AEs which the Investigator feels are incontrovertibly related to test drug. An AE may be assigned an attribution of definitely related if or when:  1. It follows a reasonable temporal sequence from administration of the test drug.  2. It could not be reasonably explained by the known characteristics of the patient's clinical state, environmental or toxic factors, or other modes of therapy administered to the patient.  3. It disappears or decreases on cessation or reduction in dose with re-exposure to drug. (Note: this is not to be construed as requiring re-exposure of the patient, however, a category of definitely related can only be used when a recurrence is observed.)		

Relationship Description		Description
		4. It follows a known pattern of response to the test drug.

AE = adverse event

## 10.3. Safety Reporting

# 10.3.1. Reporting Timelines for Adverse Events (Including Adverse Events of Special Interest)

For all patients, the AE reporting period will start with signing the pre-screening informed consent form (ICF) for AEs considered related to trial-specific procedures (for example, a biopsy).

Es occurring prior to the first study treatment are non-treatment-emergent AEs (non-TEAEs). The TEAEs are those events with onset at/or after the first study treatment. Extensive safety analysis will be mainly based on TEAEs.

#### 10.3.2. Reporting timelines for Serious Adverse events

Please refer to the Table 7 below which describes AE/SAE reporting and documentation timelines:

Table 7: Documentation and Reporting Adverse Events and Serious Adverse Events

AE/SAE	Event occurred between Pre- Screening ICF and Main ICF	Event occurred between Main ICF and 1st Infusion	Event occurred at/after 1st Infusion
AE/SAE unrelated to Study Procedure (including Pre- screening period) happens	Should not be documented	Should be documented as AE/SAE	Should be documented as AE/SAE
AE/SAE related to Study Procedure (including Pre- Screening period) happens	Should be documented as AE/SAE	Should be documented as AE/SAE	Should be documented as AE/SAE

The following information shall be captured for all AEs/SAEs: date of onset and resolution, seriousness and seriousness criteria, severity of the event, causality assessment, treatment required for the AE, action taken with study drug, and information regarding resolution/outcome.

Where known, the diagnosis of the underlying illness or disorder should be recorded, rather than listing individual symptoms.

#### 10.3.3. Reporting Serious Adverse Events and Adverse Events of Special Interest

Investigators shall report SAEs and AESIs within 24 hours of becoming aware of the event by entering all required information into the Electronic Data Capture (EDC) system by completing an electronic Case Report Form (eCRF) in accordance with the eCRF completion guidelines. Upon completion of the eCRF and submission of the eCRF, an automated notification will be triggered and will be received by the safety service provider and Sponsor.

#### 10.3.3.1. Serious Adverse Events

Other supporting documentation of the event may be requested by the Sponsor or delegate and shall be provided by the investigational site as soon as possible, personal details of the patient or site staff on those records must be fully redacted. All SAEs/AESIs will be followed up until resolution or stabilization at a level acceptable to the Investigator and/or the Sponsor.

The Investigator is not responsible for actively seeking new SAEs after the follow up period; However, if the Investigator becomes aware of an SAE that is reasonably associated with study treatment after the study period including follow up, this must be reported to the Sponsor.

#### 10.3.3.1.1. Follow-Up Information on a Serious Adverse Event

Collection of complete information concerning SAEs is extremely important. Thus, follow-up information that becomes available as the SAE evolves, as well as supporting documentation (e.g., hospital discharge summaries and autopsy reports), should be collected subsequently if not available at the time of the initial report and immediately sent using the same procedure as the initial SAE report. The Sponsor (or their delegate) will also review SAE reports for missing information and send queries to the site for resolution as appropriate. The information reported to the sponsor or delegate through a paper-based query form must be entered as well into the eCRF

to ensure consistency between the clinical and the safety database. The original signed paper-based query forms must be kept on file at the study site.

Appropriate diagnostic tests should be performed and therapeutic measures, if indicated, should be instituted. Appropriate consultation and follow-up evaluations should be carried out by the Investigator (or designee). An SAE is followed until it is considered resolved, returns to baseline, is chronically ongoing, stabilized or is otherwise explained by the Investigator.

#### 10.3.3.1.2. Reporting of Serious Adverse Events to Regulatory Authorities

In accordance with the 21 CFR 312.32, the EU Clinical Trial Regulation 536/2014 (EU-CTR), and the ICH Guidelines for Clinical Safety Data Management Definitions and Standards for Expedited Reporting, the Sponsor must submit written documentation in the form of an Investigational New Drug Application (IND) safety report or suspected unexpected serious adverse reaction (SUSAR) reports, respectively. The Sponsor should submit to the regulatory authority all safety updates and periodic reports, as required by applicable regulatory requirements. IND safety reports/SUSARs are required to be reported within 7 calendar days for life-threatening events and those resulting in death or 15 calendar days for all others. These timeframes begin with the first notification of the IND safety reports/SUSARs to the Sponsor or their delegate from the Investigator.

The Sponsor (or their delegate) will determine whether expedited reporting is necessary for SAEs depending on the assessment of seriousness, expectedness, and causal relationship. In case of disagreement between the Investigator and the Sponsor regarding causal relationship, the more conservative assessment will determine the reportability of the case.

The Investigator must ensure they are aware and comply with any additional local reporting requirements. For all SAEs regardless of expectedness and relationship, the Sponsor (or their delegate) will assign a case number to be used in all future correspondence regarding the event and can provide a MedWatch or Council for International Organizations of Medical Sciences form describing the event, for the Investigators to report to their IRB/IEC, or other committee. Other SAEs (e.g., expected or unrelated SAEs) should be reported per the relevant institution's procedures.

Where required, submission of safety updates by the Investigator to Competent Authorities must be handled according to local regulations. Otherwise, periodic safety reports to the regulatory agencies will be handled by the Sponsor (or their delegate). These safety updates will also include SAEs that do not require expedited reporting to the authorities.

Periodically (at least annually), the IB will be updated to include new and relevant safety information. Until such time that an AE becomes identified in the IB (see Summary of Data and Guidance for the Investigator), it should be considered unexpected.

#### 10.3.3.2. Adverse Events of Special Interest

#### **Infusion Related Reaction**

Occurrence of IRRs is within the anticipated safety profile of AFM24, considering experiences with other EGFR and CD16 targeting agents. Thus IRRs are realized by the sponsor as AESIs, for which ongoing monitoring and rapid communication is appropriate.

Infusion related- reactions can manifest with allergic or anaphylactic symptoms, including but not limited to chills, flushing, hypotension, fever, hypoxia, loss of consciousness, bronchospasm, and even cardiac arrest. Although the majority of such IRRs are mild to moderate, in some rare cases these can be life-threatening or even fatal. Most of the IRRs are associated with the first infusion (during or shortly after the infusion); however, IRRs can happen during or after any infusion, despite the lack of previous signs or symptoms. In the nonclinical studies of AFM24, there were no signs of IRRs or anaphylactic symptoms. For more information, refer to the latest IB edition.

IRR events require further investigation in order to characterize and understand them. Of particular interest, is information related to the timely development of symptoms relative to dose per time, actions taken as well as outcome of events. IRR events must be reported within 24 hours of awareness as per Section 10.3.3. All symptoms suggesting an IRR should be mentioned in the report.

The data will not be subject to reporting to Independent Ethics Committee (IEC)/Independent Review Board (IRB)/Regulatory Authorities unless such an event qualifies as an SAE.

## **10.3.4.** Other Reporting Obligations:

Study drug misuse, medication error, or overdose, although not categorized as "serious", shall be reported in the eCRF, even if they may not result in an adverse outcome.

- Overdose is defined as: >10% above the intended AFM24 planned dose is given or a dose interval <4 days between two consecutive doses. If the pharmacy discovers that an overdose has or may have been administered, they should contact the Investigator and Sponsor (or their delegate) immediately. In the event of overdose, the patient should be observed closely for signs of toxicity. Appropriate supportive treatment should be provided if clinically indicated.
  - In clinical trials with atezolizumab, doses of up to 20 mg/kg have been administered. The standard fixed dose of 1200 mg is equivalent to 15 mg/kg in a typical patient. No DLTs were observed at the 20 mg/kg dose level and the incidence and intensity of AEs reported have not been shown to be dependent on dose. An MTD has not been established. For this study, atezolizumab is supplied in vials containing the fixed 840 mg dose of drug substance, which minimizes the chance of overdose. Because the dose per patient is not based on weight or body surface area, and no dose calculation is required, the risk of overdose due to medication errors is minimal. The data available to date suggest that the potential for harm from overdose is very low.
- **Medication error** is defined as: An unintended failure in the drug treatment process that leads to, or has the potential to lead to, harm to the patient.
- **Misuse** is defined: Situations where an investigational medicinal product is intentionally and inappropriately used not in accordance with the terms of the current protocol.

If any of the above events is associated with an SAE, it must be reported within 24 hours as per Section 10.3.3.

#### **10.3.4.1.** Exposure During Pregnancy or Lactation

Pregnancy and breastfeeding are considered exclusion criteria for this study (Section 5.2). Although pregnancy and lactation are not considered AEs, it is the responsibility of Investigators or their designees to report any pregnancy or lactation in a patient (spontaneously reported to them) or pregnancy in a patient's partner that occurs during the study. Immediately discontinue AFM24 treatment permanently in case of pregnancy.

Pregnancies and lactations that occur in patients after the ICF is signed but before starting study drug must be reported by the Investigator if they cause the patient to be excluded from the study.

Pregnancies and lactations that occur in a study patient or a pregnancy in a patient's partner from the time of first study treatment through up to 60 days following cessation of AFM24 study treatment, must be reported by the Investigator.

All reported pregnancies must be followed to the completion or termination of the pregnancy. If the pregnancy continues to term, the outcome, i.e., the health of the infant, will be requested by the Sponsor. Parental and neonatal outcomes must be recorded even if they are completely normal and without AEs. Offspring should be followed up for at least 8 weeks after delivery. Longer observation periods may be determined by the Sponsor if an adverse outcome of the pregnancy was observed.

Such events must be reported within 24 hours to the Sponsor or delegate as per Section 10.3.4.1. The reporting procedures can be found in the SAE completion guidelines located in the Study Operations Manual (or equivalent).

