- 11) Females of childbearing potential must agree to sexual abstinence (defined below) or be willing to use a highly effective method of contraception for the course of the study from 14 days prior to the first dose of study drug through 5 months after the last dose of study drug. Acceptable highly effective birth control methods include:
  - a. Oral, intravaginal, or transdermal combined (estrogen and progestogen containing) hormonal contraception associated with inhibition of ovulation;
  - b. Oral, injectable, or implantable progestogen-only hormonal contraception associated with inhibition of ovulation;
  - c. Intrauterine device;
  - d. Intrauterine hormone-releasing system;
  - e. Bilateral tubal occlusion;
  - f. Vasectomized partner (provided that partner is the sole sexual partner of the female of reproductive potential and that the vasectomized partner has received medical assessment of the surgical success); and
  - g. Sexual abstinence. In the context of this study sexual abstinence is considered a highly effective method only if defined as refraining from heterosexual intercourse from 14 days prior to the first dose of study drug up to 5 months after the last dose of study drug. The reliability of sexual abstinence needs to be evaluated in relation to the duration of the clinical study and the preferred and usual lifestyle of the patient.
- 12) Males who have female partners of childbearing potential must agree to use a highly effective method of contraception as described in Inclusion Criterion 11) starting with the first dose of study therapy through 5 months after the last dose of study drug.

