## **Atezolizumab**

Continuation of therapy on-study in the setting of discontinuation of one component (AFM24 or Atezolizumab) of the study therapy

If one component of the study therapy is permanently discontinued secondary to toxicity, then therapy with the other component may continue at the discretion of the investigator and the patient should remain on-study with full adherence to all protocol-related requirements, provided the patient continues to meet entry criteria and does not have evidence of disease progression.

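### The explicit pregnancy-reporting window ends 60 days after AFM24, about three months before the contraception period, which runs from the last dose of study drug

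*Protocol*

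**What the plan says.** **Reporting.** Protocol Section 10.3.4.1 contains two rules. The general one makes investigators responsible for reporting a pregnancy or lactation in a patient, if it is spontaneously reported to them, or a "pregnancy in a patient's partner that occurs during the study". It gives no end date. The specific one sets the window for mandatory reports: "from the time of first study treatment through up to 60 days following cessation of AFM24 study treatment". Its end point depends on AFM24 only.

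**Contraception.** Section 5.1, repeated in the synopsis, sets a longer period. For women of childbearing potential (criterion 11) it runs "from 14 days prior to the first dose of study drug through 5 months after the last dose of study drug". For men with partners of childbearing potential (criterion 12) it runs "starting with the first dose of study therapy through 5 months after the last dose of study drug". Section 10.2.3 (Causality Assessments) counts AFM24, atezolizumab and their combination as study drug.

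**One drug without the other.** Under Section 6.7 (Atezolizumab), if one component is permanently stopped for toxicity, "then therapy with the other component may continue at the discretion of the investigator and the patient should remain on-study". This requires that entry criteria are still met and that there is no progression.

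**The concern.** A contraception requirement and a pregnancy-reporting window normally cover the same period, so that a pregnancy arising despite the requirement is reported and followed. Here the reporting window is shorter and is tied to one of two drugs. A site that follows the specific rule as written need not report a pregnancy that begins more than 60 days after AFM24 stops, even though the contraception requirement is still in force and atezolizumab may have been given more recently.

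What is at stake is safety information on exposed pregnancies. Section 10.3.4.1 wants every reported pregnancy followed to its end and the outcome recorded even when it is normal, which presupposes that the pregnancy is reported in the first place.

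**Working it through.** The plan has no figure of its own to reproduce. The check compares the windows and counts days.

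**Inputs**
- Reporting window after AFM24: 60 days (Section 10.3.4.1).
- Contraception after last study drug: 5 months (Section 5.1, criteria 11 and 12), or 5 × 365.25/12 = 152 days. Depending on the calendar months, this is 150 to 153 days.
- Half-lives: AFM24 11.2 days at doses of 320 mg or more (Section 2.2.3); atezolizumab 27 days (Section 2.3.1).
- W, the weeks on atezolizumab alone after the last AFM24 dose, is not given in the documents. The values below are illustrative assumptions.

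**1. Both drugs stop on the same day.** Days of the contraception period outside the explicit window = 152 − 60 = 92 (range 90 to 93), and 92/152 is about 61%. This is a share of calendar days, not of pregnancies. The same 92 days apply if AFM24 is the drug that continues alone.

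**2. Atezolizumab continues alone for W weeks.** Days outside the explicit window = 7W + 92. Of these, days still on atezolizumab = max(0, 7W − 60).

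| W (weeks) | Days outside the explicit window | Of these, still on atezolizumab |
|---|---|---|
| 0 | 92 | 0 |
| 4 | 120 | 0 |
| 8 | 148 | 0 |
| 12 | 176 | 24 |
| 24 | 260 | 108 |

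The explicit window closes during dosing once 7W exceeds 60, that is, W above about 8.6 weeks.

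**3. Why the anchor matters.** Assuming first-order elimination, the fraction remaining is 0.5^(days/half-life).
- AFM24 at 60 days: 60/11.2 = 5.4 half-lives, about 2% left.
- Atezolizumab at 60 days: 60/27 = 2.2 half-lives, about 21% left.
- Atezolizumab at 5 months: 152/27 = 5.6 half-lives, about 2% left.

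The 60-day limit thus leaves about as little AFM24 as the 5-month period leaves atezolizumab. This suggests, without proving it, that the reporting sentence was written for AFM24 alone. The same section names only AFM24 for discontinuation in pregnancy, whereas Section 5.4.2 refers to study drug.

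**4. Whether the general duty fills the gap.** Section 4.5 ends the study when all patients have completed the first long-term follow-up interval, withdrawn or died. Section 4.1 sets contacts every 3 months ± 2 weeks and a safety visit at 30 ± 5 days. If the interval is counted from the safety visit, the latest completion is 35 + 91 + 14 = 140 days after the last dose, which is less than 152. For the last patients, the study can therefore end before the 5 months are over.

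**The case against.** The strongest case on the other side is that the general duty in Section 10.3.4.1 already applies and is tied neither to AFM24 nor to 60 days. A patient on atezolizumab alone stays on-study under Section 6.7. Section 5.4.2 makes pregnancy on study drug a reason for withdrawal, and Section 10.1.1 repeats the withdrawal and refers to Section 10.3.4.1 for reporting. Late adverse outcomes also have a route: a congenital anomaly is an SAE (Section 10.1.2), and an SAE reasonably associated with treatment must be reported even after follow-up if the investigator learns of it (Section 10.3.3.1).

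Most of this stands. A reader might infer that pregnancies are reportable only up to 60 days after AFM24, that the gap is open-ended for anyone staying on atezolizumab, or that exposed pregnancies and their outcomes would go uncollected. The documents support none of these. A pregnancy during atezolizumab alone is probably reportable under the general duty, and known serious outcomes are reportable without a time limit. Nor does the protocol call the 5 months a period of fetal risk; the visible text gives a contraception requirement without a stated reason.

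The objection does not remove the conflict. The general duty stands beside a specific and narrower limit, and a site may reasonably follow the specific one. For patients it relies on spontaneous reporting, it has no defined end after the last dose, and it can lapse before 5 months under the end-of-study rule. The SAE route captures adverse outcomes that become known, not pregnancies as such.

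**Conclusion.** The inconsistency is real and should be corrected. With both drugs stopped together, about 92 of about 152 days of required contraception fall outside the explicit reporting window. With atezolizumab alone for more than about 8.6 weeks, the explicit window closes during treatment, although the general duty probably still applies then.

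The day counts assume that cessation of AFM24 means its last dose and that a month has its average length. How often atezolizumab will continue alone is unknown. It requires a toxicity stop, investigator discretion, continued eligibility and no progression, and it is excluded after a Cycle 1 DLT in Phase 1, where both drugs must stop (Section 4.2.3.1). Few pregnancies are to be expected in patients with advanced cancer under mandatory contraception.

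The SAE completion guidelines that Section 10.3.4.1 cites were not available and may narrow the gap in practice. This is a safety-reporting matter; sample size, power and the planned analyses are untouched.

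**What to change.** Reconcile Sections 10.3.4.1, 5.1 (criteria 11 and 12) and 6.7 in the next amendment. Rewrite the reporting sentence so that the window runs from the last dose of either study drug and ends when the protocol's existing contraception period ends, for patients and partners alike. State how the general duty relates to this window, so that sites have one rule. Make the same change in the safety reporting guideline.

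The cost is one sentence, the guideline edit and a few extra reports. The three-monthly long-term contacts already exist and could carry the question. Patients who stop in the safety lead-in have no long-term follow-up (Section 4.2.5), so for them a late report would still depend on the patient informing the site. The change alters no dose, schedule or treatment rule.
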